2.6 Background Clinical

2.6.1 Previous Clinical Trials of Allogeneic Mesenchymal Stem Cells (allo-MSCs)

Allo-MSCs have been used in several recent FDA-approved trials. **The cumulative experience in these studies demonstrates an outstanding safety margin and a significant potential for cardiac regeneration.**

In a multi-center, randomized, double-blinded, placebo-controlled clinical study by Hare et al. 53 patients with recent acute MI (3 to 10 days) were treated with allo-MSCs (0.5, 1.6 and 5.0 cells/kg, corresponding to 3.5×10^7 , 1.1×10^8 , and 3.5×10^8 cells per patient for a 70 kg body weight patient), or placebo administered via peripheral intravenous injection, and followed for six months⁸⁷. There were no deaths reported in the study; no toxicity was observed with the administration of the allo-MSCs (which were found to be well-tolerated at all dose levels administered, with 5.3 adverse events per patient in the MSC-treated group vs. 7.0 in the placebo group); and no serious adverse events were attributed to MSC administration. The group of patients treated with MSCs demonstrated reduced ventricular tachycardia episodes ($P=0.025$), and pulmonary function testing demonstrated improved forced expiratory volume in 1 s ($P=0.003$) in the MSC-treated patients. In addition, left ventricular ejection fraction (LVEF) in the important subset of anterior MI patients was significantly better in MSCs versus control subjects, with a 7.3% absolute improvement in EF at 6 months over baseline. In the cardiac MRI substudy, MSC treatment, but not placebo, increased LVEF and led to reverse remodeling.

The POSEIDON trial was a phase 1/2 randomized controlled study in which 30 patients with chronic ischemic cardiomyopathy were randomized to 20 million, 100 million, or 200 million autologous MSCs or allo-MSCs (5 patients were given each cell type for each dose of cells)⁵⁶. The cells were delivered by transendocardial injection into 10 LV sites in a volume of 0.5 mL for each injection. The primary outcome was incidence of severe adverse events at 30 days. At 1 year, there was no difference between allogeneic and autologous MSCs with regards to serious adverse events. In addition, at 1 year, there were no ventricular arrhythmia serious adverse events (SAEs) observed among allo-MSC recipients compared with 4 patients (26.7%) in the autologous MSC group ($P = .10$). Although there was no significant improvement in LVEF in any group, there was a sizeable reduction in scar size in both allogeneic and autologous groups. Importantly, allo-MSCs did not stimulate significant donor-specific allo-immune reactions.

The CTSN LVAD study⁸⁸ was an NHLBI-sponsored multi-center, double-blind, sham-procedure controlled trial to assess the safety and feasibility of MSC implantation into the LVAD-assisted heart. Thirty patients were randomized (2:1) to intramyocardial injection of 25 million mesenchymal precursor cells (MPCs) (Mesoblast, Inc.) or medium during LVAD implantation and followed until transplant or 12 months whichever came first. No safety events were observed. At 90 days, successful temporary LVAD weaning was achieved in 50% of MPC and 20% of control patients ($P=0.24$). Three deaths (30%) occurred in control patients and none occurred in MPC patients. Mean left ventricular ejection fractions after successful wean were 24.0% (MPC=10) and 22.5% (control=2; $P=0.56$). At 12 months, 30% of MPC patients and 40% of control patients were successfully temporarily weaned from LVAD support ($P=0.69$), and 6 deaths occurred in MPC patients. Donor-specific HLA sensitization developed in 2 MPC and 3 control patients and resolved by 12 months.

In addition, Perin et al. (NCT00721045) investigated the safety of allo-MSCs in the setting of acute MI. This study was supported by Mesoblast and performed at six centers in the US between 8/2008 and 5/2010 to assess the safety and effect of bone marrow derived allogeneic MPC's STRO-1bright cells on LV function. This was a Phase II, single-blind, randomized, dose-escalation study of 60 subjects with fifteen subjects per group exploring three doses of cells (i.e., 25 million, 75 million or 150 million). Subjects were injected via the transendocardial route utilizing the NOGA system into viable myocardium. Outcomes were a) immunological safety; b) safety of the injection procedure; c) 6-month surrogate efficacy findings of no change in LVEF and 6-minute walk test (control corrected 34 meters' improvement but not significant in the 150 million cell group), significant decrease in both left ventricular end systolic volume (LVESV) and end diastolic volume (LVEDV) in the 150 million group; and d) MACE evaluations to 36 months in all groups. For ischemic MACE (i.e., death, MI and revascularization), pooled MPC had significantly lower events but no significant difference between any cell dose group and control patients. For heart failure (HF) MACE (i.e., cardiac death or HF re-hospitalization) there were no events in the 150 million cell group, and there were no significant differences between any cell dose group and control patients. For all events, there were 12 events in total combined three cell groups (n=45) compared with 11 events in the control group (n=15). These are unpublished data, partially presented at AHA 2013 and currently submitted and under review for publication.

Taken together, these trials of allo-MSCs demonstrate not only an excellent safety profile of this therapy but also a considerable potential for allo-MSCs to exert beneficial effects in patients with heart failure^{56,87}.

2.6.2 Ongoing/Future Clinical Trials of Allogeneic Mesenchymal Stem Cells

There are several ongoing studies of allo-MSCs in cardiac diseases. The safety study of *Allogeneic Mesenchymal Precursor Cell Infusion in MyoCardial Infarction (AMICI)* (NCT01781390) is a multi-center randomized clinical trial in which 225 patients with new acute MI in the left anterior descending (LAD) artery territory are randomized to intracoronary infusion of 12.5 or 25 million allo-MSCs or placebo (cells are injected at the time of primary coronary intervention).

Allogeneic stem cells are also under investigation in patients with dilated cardiomyopathy (DCM). *PercutaneOus StEm Cell Injection Delivery Effects On Neomyogenesis in Dilated CardioMyopathy (the POSEIDON-DCM Study)* (NCT01392625) is an ongoing study that is actively recruiting 36 patients with DCM and randomizing to receive autologous MSCs vs. allo-hMSCs via intramyocardial injection; patients will receive 100 million MSCs (autologous or allogeneic) delivered in 10 injections via the transendocardial route utilizing the NOGA system.

2.6.3 Previous Clinical Experience with Intramyocardial Delivery of Stem Cells

There is substantial clinical experience with the transendocardial delivery of autologous bone marrow-derived mononuclear cells (BMCs) as well as autologous MSCs and allo-MSCs in the setting of chronic LV dysfunction. The aforementioned POSEIDON trial⁵⁶, the TAC-HFT trial⁸⁹, the FOCUS-CCTRN trial⁹⁰ and the RENEW trial (NCT01508910), are only a few examples of the application of this delivery method for cell therapy in patients with cardiovascular disease. In addition, multiple ongoing trials are using intramyocardial injection as the mode of delivery for stem cells. Table 1 (see below) lists the 11 studies in which intramyocardial delivery of BMCs was performed⁹¹⁻¹⁰¹. Cell delivery has been performed via either i) direct intramyocardial (IM) injection during coronary artery bypass graft (CABG) surgery, or ii) catheter-based

CONFIDENTIAL AND PROPRIETARY

intramyocardial injection (transendocardial delivery). Taken together, these studies clearly support the clinical safety of the intramyocardial injection delivery method.

Table 1. Studies utilizing Intramyocardial Delivery of BMCs

Study	N	Cell Delivery Method	Cell Source & Type	Cell Doses (x 10 ⁶)	Safety	Efficacy Results
Stamm ⁹⁹	6	Direct IM injection during CABG surgery	Autologous, AC133* BMCs	1.2 - 3.4	No arrhythmias; no neoplasia	↑ global contractility (EF)
Tse ¹⁰¹	8	Catheter-based IM injection	Autologous BMCs	2.6 – 21.2	No arrhythmias	↑ wall motion & thickening
Fuchs ¹⁰⁰	10	Catheter-based IM injection	Autologous BMCs	32.6 ± 27.5	No arrhythmias or other SAEs	↓ angina score; ↓ ischemia
Perin ⁹⁷	14	Catheter-based IM injection	Autologous CD34* BMCs	25.5 ± 6.3	No arrhythmias at 6-mo. F/U	↑ global contractility (EF); ↓ ESV
Beeres ⁹¹	25	Catheter-based IM injection	Autologous BMCs	84.1 + 28.7	No arrhythmias or pericardial effusion	↑ global contractility (EF); ↓ ESV
Briguori ⁹²	10	Catheter-based IM injection	Autologous CD34* BMCs	4.6 ± 1.5	No arrhythmias or AMI	↑ quality of life; ↑ perfusion
de La Fuente ⁹³	10	Catheter-based IM injection	Autologous CD34* BMCs	86 ± 3	No arrhythmias at 12-mo. F/U	↑ global contractility (EF)
Mocini ⁹⁶	36	Direct IM injection during CABG surgery	Autologous CD34* BMCs	292 + 232	No SAEs	↑ global contractility (EF)
Hendrikx ⁹⁴	20	Direct IM injection during CABG surgery	Autologous BMCs	60.1 ± 31.1	Possible inducible VT	↑ global contractility (EF)
Stamm ⁹⁸	55	Direct IM injection during CABG surgery	Autologous, CD133* BMCs	3.85 – 103.0	No arrhythmias	↑ global contractility (EF)
Li ⁹⁵	6	Direct IM injection during CABG surgery	Autologous BMCs	50 - 100	No arrhythmias; no neoplasia	Not Assessed

AMI: acute myocardial infarction; IM: intramyocardial; CABG: coronary artery bypass graft; BMC: bone marrow-derived mononuclear cells; EF: Ejection Fraction; ESV: end systolic volume; F/U: follow-up; SAE: serious adverse event; VT: ventricular tachycardia

The proposed transendocardial injection system, the NOGA MyoStar injection system, has been utilized in multiple clinical trials of transendocardial injection including, but not limited to, the ACT34-CMI¹⁰², FOCUS-HF¹⁰³, FOCUS-CCTR⁹⁰, RENEW (NCT01508910), and NOGA-DCM¹⁰⁴ studies. Again, this vast experience has shown this system to be safe, with minimal SAEs. In a retrospective safety study of the NOGA MyoStar injection system, data from 71 patients who had undergone intramyocardial mapping and/or injection in the context of clinical trials were pooled and analyzed¹⁰⁵. Although there were no major complications, NOGA

CONFIDENTIAL AND PROPRIETARY

mapping followed by direct intramyocardial injections led to CK-MB rises exceeding three times the upper limit of normal in 8 patients (17%) who received a volume of 0.3 mL per injection, compared with none in NOGA mapping alone¹⁰⁵.

2.7 Dose and Delivery Rationale

2.7.1 Dose Rationale

The clinical experience with the administration of MSCs in the trials performed to date provides substantial evidence of safety at cell doses up to 200 million MSCs as well as preliminary evidence of efficacy. In SENECA, we propose to administer a total of 100 million allo-MSCs, divided into 20 injections of 5 million cells each. A dose of 100 million MSCs delivered transendocardially has already been used in clinical trials, namely, the POSEIDON⁵⁶ and TAC-HFT trials⁸⁹, and found to be safe. This dose is within the range of doses (20 to 200 million MSCs) used in previous human studies of MSCs^{56,89}. In the ongoing POSEIDON-DCM trial (NCT01392625), a dose of 100 million allo-MSCs is being used. The rationale for selecting 100 million cells is that in the POSEIDON trial⁵⁶, there was an inverse dose response, leading the authors to speculate that higher doses may be less efficacious due to deleterious effects on cell retention, survival, or performance.

Preclinical investigations are also consistent with an inverse dose response. Hamamoto et al. demonstrated in an ovine model of acute MI treated with transendocardial injection of 25, 75, 225, and 450 million STRO-3 MSCs that, compared with control animals, low doses (25 and 75×10^6 cells) of MSCs significantly attenuated the increase in LV end diastolic (LVEDV) and end systolic (LVESV) volumes; the 225 million dose improved only the LVESV over control, whereas the 450 million dose did not produce any salutary remodeling effect relative to controls¹⁰⁶. In addition, infarct expansion was attenuated only in the 25, 75, and to some extent the 225 million groups although EF improved at all cell doses. CD31 and smooth muscle actin (SMA) immunohistochemical staining demonstrated increased vascular density in the border zone only at the two lower cell doses (more so in the 75 million group albeit, statistically insignificant between 25 and 75 million cell groups)¹⁰⁶. Another ovine study used a protocol and allo-MSC doses similar to the above study and found that the LVEDV increase was significantly attenuated only in the 25 and 75 million groups compared with controls whereas the drop in EF was uniform across all doses of allo-MSCs in comparison to the control animals ($P < 0.05$)¹⁰⁷; both findings in Dixon et al.¹⁰⁷ were analogous to the findings by Hamamoto et al¹⁰⁶.

2.7.2 Delivery Rationale

The choice of the transendocardial delivery route is based on both preclinical and clinical data. In a preclinical study, Psaltis et al. (2010) demonstrated in an ovine model that cell therapy delivered by the NOGA device is safe and effective in the treatment of doxorubicin-induced cardiomyopathy⁸⁶. Moreover, there is substantial clinical experience in humans with the transendocardial delivery of autologous bone marrow-derived mononuclear cells (BMCs) as well as autologous MSCs and allo-MSCs in the setting of chronic LV dysfunction. POSEIDON⁵⁶, TAC-HFT⁸⁹, FOCUS-HF¹⁰³, FOCUS-CCTR⁹⁰, RENEW (NCT01508910), NOGA-DCM¹⁰⁴, and Perin et al.'s study (NCT00721045) clearly demonstrate that NOGA can be carried out safely in humans with cardiomyopathy. Table 1's tabulation of the numerous studies utilizing direct intramyocardial injection adds to the weight of favorable clinical experience with this technique. Intracoronary delivery of allo-MSCs is not recommended in our protocol because of the likelihood, or at least the possibility, of producing microvascular obstruction with resultant dose dependent myocardial damage^{108,109}. In addition, no published clinical trial supports the efficacy

CONFIDENTIAL AND PROPRIETARY

of intracoronary MSC delivery, in contrast to the copious literature supporting the efficacy of transendocardial MSC delivery as discussed previously.

Studies by Tham¹¹⁰ and Steinherz⁵ demonstrate that fibrosis in AIC patients is diffuse with a unique cardiac MRI profile. Our injections will target areas of diffuse fibrosis. The use of NOGA technology in preclinical models of anthracycline-induced cardiomyopathy, as well as idiopathic dilated cardiomyopathy, justifies its use in this protocol. Taken together, the available literature and ongoing experience support the clinical safety of the intramyocardial injection delivery method and suggest that this route of cell administration is efficacious.

3.0 STUDY DESIGN

3.1 Research Questions

- **Question 1:** Are allo-MSCs well-tolerated by subjects with LV dysfunction secondary to AIC?
- **Question 2:** Can allo-MSCs be delivered to subjects with LV dysfunction secondary to AIC, and can the outcome measures be collected?
- **Question 3:** Do allo-MSCs produce a trend toward improved LV function and functional status when compared with placebo from baseline to six months and/or from baseline to 12 months post treatment with study product?

3.2 Study Design

This study will evaluate approximately thirty-six subjects. The first six subjects will receive allo-MSC therapy (open label) and will be assessed for safety and feasibility of the study procedures. Following 1 month data review of each of the six subjects by the NHLBI Gene and Cell Therapy Data and Safety Monitoring Board; this will be followed by a randomized, double-blind clinical trial enrolling approximately thirty subjects (see Section 7.7). These subjects will be randomized 1:1 to receive allo-MSCs or placebo. All subjects will undergo cardiac catheterization and study product administration using the NOGA Myostar catheter injection system. Subjects will be followed at 1 day, 1 week, 1 month, 6 months, and 12 months post study product injection. All endpoints will be assessed at the 6 and 12 month visits which will occur 180 ± 30 days and 365 ± 30 days, respectively, after the day of study product injection (Day 0).

For the purpose of the safety evaluations and endpoint analysis, we will utilize an “intention-to-treat” study population. In addition, because this phase I study is the first cell therapy study in this population, at 12 months all available standard-of-care medical records for cancer surveillance will be reviewed for cancer recurrence. Approximately thirty-six subjects will be enrolled over a 12-18 month accrual period.

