1.3 Hypotheses

Ho 1: Allo-MSCs delivered transendocardially in subjects with LV dysfunction, secondary to AIC, are well-tolerated.

Ho 2: Allo-MSCs can be delivered to subjects with LV dysfunction, secondary to AIC, and the outcome measures can be collected.

Ho 3: Compared with placebo, allo-MSCs promote myocardial repair, thereby producing a trend toward reduced scar burden and improved cardiac performance, functional capacity, and quality of life from baseline to six months and/or from baseline to 12 months post treatment with study product.

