4.6 Randomization Procedures and Timing

Randomization to treatment assignment (cells or placebo) will be conducted using a web access database created and maintained by the Data Coordinating Center (DCC). The research coordinator (RC) will randomize the subject via the CCTRN web-based database which will perform the computer-generated randomization assignment and send automatic emails notifying the study team that the treatment assignment can be accessed by unblinded study team members with appropriate security credentials. The RC will not randomize the subject until the following criteria are met: i) the subject has provided written informed consent, ii) baseline evaluations are complete, iii) the inclusion and exclusion criteria for the study have been satisfied, and iv) MSC product is available at the cell manufacturing facility (CMF) should the subject be randomized to the cell group. Randomization should occur no less than 3 days prior to the scheduled SPI procedure (to allow time for cell shipping and local product preparation) and no more than 7 days prior to the scheduled SPI procedure (to minimize the risk of randomizing subjects who do not receive treatment).

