8.2 Delays and Early Withdrawal from the Study

There may be circumstances in which randomized subjects experience a delay in receipt of study product. There may also be circumstances that do not allow for randomized subjects to receive study product. These circumstances are discussed further below. All randomized subjects who do not receive SPI in the expected timeframe will have their case reviewed by the Medical Monitor and SENECA Center PI to assess whether the subject should be withdrawn immediately or delay study procedures for another attempt.

Circumstances that may result in delaying SPI could be related to a change in the clinical condition of the subject or to an issue with local cell processing and product preparation.

1. A randomized subject who has a resolvable change in their clinical condition, and for whom the product has not yet been prepared for injection, will be allowed to have their SPI postponed.

2. If a cell processing related issue arises on the day of the SPI procedure and additional product can be delivered at a later time, the subject will have their SPI postponed.

Length of postponement will be determined by the Medical Monitor and SENECA Clinical Center PI upon review of the case details. The subject must remain eligible for the study in order to proceed with SPI, which may include repeat baseline testing. A subject who cannot be treated will no longer qualify for inclusion in the study, though will be included in all analyses for which they have data in accordance with the "intention-to-treat" principle.

In this first-in-human, phase I trial, SENECA's principal analysis will be "intention-to-treat". The anticipated small number of patients who are randomized but do not receive treatment will have the reason for non-treatment tabulated.

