8.3.2 Outcome Analyses

All analyses will be performed on two cohorts; (1) the randomized cohort, and (2) the total cohort (randomized plus the six patients who received open label therapy in a nonrandomized fashion).

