9.1.2.2 Cell Processing

For those patients receiving the allo-MSC cell product, it is possible that the body might react and reject the allo-MSC cells. Human clinical research studies with allo-MSCs in heart patients have provided evidence against the occurrence of rejection of the transplanted cells and also against the occurrence of GVHD, where healthy infused cells recognize the tissues of the person receiving the cells as "foreign" and mount an immunologic attack.

Processing the cells is done under strict sterile conditions; however, there is a rare chance that the cells could get contaminated while being processed. Testing will be done on the cells; however, it takes about 2 weeks to get the final results. If the tests show cells were contaminated, the treatment team will be notified so that the patient may be treated with antibiotics. Subjects will be taking their temperature twice a day for one week, which may help determine infection before the test results are known.

There may be some circumstances where the patient is unable to receive the processed cells; such as a processing failure or poor quality of the cells. If events such as these occur, the patient will not receive the allo-MSC cells but will be asked to continue with follow up in the study. Processes in place to prevent these failures include: the use of standard operating procedures for preparing the allo-MSC cell product, which will identify any problems with the study product before it is released, and continuous temperature monitoring of the product during shipment to the treatment facility.

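### Safety is analysed only on intention-to-treat cohorts, with no exposed safety set; never-treated subjects can bias the arm rates in either direction

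*Combined protocol and SAP*

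**What the plan says.** Section 3.2 sets one population for safety and efficacy: "For the purpose of the safety evaluations and endpoint analysis, we will utilize an" intention-to-treat population. Section 8.2 repeats that "SENECA's principal analysis will be" intention-to-treat, and says of a subject who cannot be treated that he or she no longer qualifies for the study, "though will be included in all analyses for which they have data in accordance with the" intention-to-treat principle. It adds: "The anticipated small number of patients who are randomized but do not receive treatment will have the reason for non-treatment tabulated".

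Section 8.3.2 names the analysis sets: "All analyses will be performed on two cohorts; (1) the randomized cohort, and (2) the total cohort", the second adding the six open-label subjects. Neither is defined by receipt of study product. Section 8.3.2.1 compares safety by therapy group with Fisher's exact test, from baseline to 6 and to 12 months.

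The first hypothesis in Section 1.3 is about exposure: "Allo-MSCs delivered transendocardially in subjects with LV dysfunction, secondary to AIC, are well-tolerated". Section 9.1.2.2 foresees processing failure or poor cell quality, in which case "the patient will not receive the allo-MSC cells but will be asked to continue with follow up in the study".

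**The concern.** The primary safety question is what happens to people who undergo the procedure and receive the cells. The planned sets answer a different question: what happens to people assigned to them. The two differ for any randomised subject who is never treated, and the plan expects some.

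Such a subject affects the safety table in two ways. For tamponade after an injection, or hypersensitivity to the product, the subject counts in the denominator but can never enter the numerator, so the rate falls. For an event after consent but before any procedure, the assigned arm is charged with something its treatment did not cause, so the rate rises.

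The first effect is more likely in the cell arm. Cells are shipped frozen (Section 5.1.1) and must pass viability and cell-count tests (Table 2a). Placebo is held on site and has neither test (Section 5.2, Table 2b). With about 15 subjects per arm in a first-in-human trial, one or two subjects can change how a safety table reads.

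**Working it through.** **Inputs from the plan.** Cell arm 15 randomised (Executive Summary), or 15 + 6 = 21 with the lead-in; Fisher's exact test (Section 8.3.2.1); nominal 0.05 level and a 95% interval for the effect size (Section 8.6). The plan gives no safety event rate, no per-arm limit and no number untreated, so there is no plan figure to reproduce on this point.

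**Assumptions.** The number m of untreated cell-arm subjects is 1, 2 or 3. Limits are two-sided 95% Clopper-Pearson; tests are two-sided.

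**1. Untreated subjects are event-free, and the event is one that only injection or cells can cause.** The intention-to-treat rate is (15 − m)/15 of the rate among the treated: 14/15, 13/15 or 12/15, that is 7%, 13% or 20% too low. For zero events the upper limit is 1 − 0.025^(1/n); for n = 15 this is 1 − 0.025^(1/15) = 21.8%.

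| Events | ITT upper limit | m = 1 | m = 2 | m = 3 |
|---|---|---|---|---|
| 0, denominator 15 | 21.8% | 23.2% | 24.7% | 26.5% |
| 3, denominator 15 | 48.1% | 50.8% | 53.8% | 57.2% |
| 0, denominator 21 | 16.1% | 16.8% | 17.6% | 18.5% |

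With zero events among 15, the limit is too low by 1.4, 2.9 or 4.7 points. In the total cohort the differences are 0.7, 1.5 and 2.4 points.

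**2. One untreated subject has a counted event before the procedure.** Intention-to-treat gives 1/15, upper limit 31.9%; the treated give 0/14, upper limit 23.2%. With one further event among the treated, it is 2/15 (40.5%) against 1/14 (33.9%). The direction has reversed.

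**3. Effect on the planned test, four events against none.**
- 4/15 v 0/15: p = 2 × C(15,4)/C(30,4) = 2 × 1365/27405 = 0.0996.
- 4/14 v 0/15 (one untreated, cell arm only): p = C(14,4)/C(29,4) = 1001/23751 = 0.042.
- 4/14 v 0/14 (one untreated in each arm): p = 2 × 1001/20475 = 0.098.

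Much of the drop in the second case comes from the discreteness of the two-sided test. With unequal arms, the opposite extreme (1365/23751 = 0.057) is more probable than the observed table and no longer counts. The single-tail value moves only from 0.0498 to 0.0421. The example shows how fragile the p-value is at this size, not that the evidence has changed much.

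**The case against.** A reader might infer that intention-to-treat always flatters the cells on safety, and that an injected-only set should replace it. The documents do not support either step.

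- **Direction.** Event reporting starts at consent (Section 7.3), and the first feasibility measure counts events that prevent injection (Section 3.4.2). Step 2 shows such an event makes intention-to-treat the harsher analysis.
- **Uninjected does not mean unharmed.** Mapping precedes injection (Section 5.4). Section 9.1.2.1 lists perforation, stroke, ventricular arrhythmia and death among its risks, and Section 5.5 provides for halting before or during injection. A set requiring at least one injection would drop a subject perforated during mapping.
- **Scope.** Death, heart-failure events, stroke, neoplasm and grade 2 or higher adverse events can all occur without injection. The 7% to 20% dilution does not apply to them in general.
- **Imbalance.** Placebo can also fail its Gram stain or endotoxin test (Table 2b). Product must be available before randomisation, which takes place 3 to 7 days before injection to limit non-treatment (Section 4.6). Some day-of-procedure processing problems lead to postponement (Section 8.2).
- **Statistic.** Section 8.6 plans an interval for the effect size; the per-arm limit above is an illustration. The reported reasons for non-treatment and the doses delivered let a reader partly rebuild the denominator.

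All of this stands. It removes any claim of a fixed favourable bias and any case for displacing intention-to-treat. It does not supply the missing exposed analysis: the feasibility counts do not show adverse events by exposure.

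**Conclusion.** The gap is real and modest. Safety is planned on two assignment-based cohorts only, while the first hypothesis concerns delivered cells. For events that only injection or cells can cause, untreated subjects dilute the rate, more likely in the cell arm; for pre-procedure events, the assigned arm is overcharged. The net direction cannot be known in advance.

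With zero events, the illustrative shift is 1.4 to 4.7 points on an upper limit of 21.8%. This rests on 1 to 3 of 15 cell-arm subjects being untreated, event-free and still in the denominator. The plan says only that a small number is expected, and 3 of 15 is the outer end of what was assumed, not a forecast. The between-arm comparison changes appreciably only if non-treatment is unequal between arms.

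One related point needs reconciling. Section 8.2 allows immediate withdrawal of an untreated subject, while Section 9.1.2.2 asks such a patient to stay in follow-up. Visit windows run from the injection day (Section 6.5.7), so the 6- and 12-month periods are undefined for that subject.

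**What to change.** Keep the intention-to-treat safety comparison, which preserves the randomised contrast. Beside it, prespecify an exposed safety analysis:

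- Include every subject in whom the study catheterisation/NOGA procedure was started.
- Group by product actually injected, and show subjects who had the procedure but no injection separately.
- Count events from the start of the procedure, so that mapping complications are retained.
- List events between randomisation and the procedure separately.
- Give exact 95% limits for each group's event proportions.

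State also which start date defines the 6- and 12-month periods for untreated subjects in the intention-to-treat table. Efficacy sets and feasibility measures need no change.

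The cost is a paragraph in Section 8.3.2, one extra set of tables and slightly smaller denominators. The exposed comparison is not fully protected by randomisation, which is why it should accompany the intention-to-treat table and not replace it.
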